# **6. STUDY PROCEDURES AND ASSESSMENTS**

## **6.1. Visit 1**

### **6.1.1. Informed consent and screening**

#### **6.1.1.1. Informed Consent**

The study staff will obtain written informed consent from the participant in-person or over a video conference call with the participant. Written consent must be obtained from all participants and documented on an Informed Consent form (ICF) that has received approval by an IRB/Ethics Committee. The ICF will be written in adherence to Good Clinical Practice (GCP) and must comply with all elements required by United States (U.S.) Food and Drug Administration (FDA) 21 CFR 50.25 and International Conference on Harmonization (ICH) 4.8, state and local regulations, and additional elements relevant to specific study situations (including a statement that Medline Industries, LP and relevant authorities have access to participant records). A copy of the signed consent will be provided for each participant.

#### **6.1.1.2. Verification and Eligibility**

The PI or delegated study staff will verify the eligibility of the individual for the study, based on the inclusion and exclusion criteria that will be evaluated in the Participant Screening Form. Participant demographics (age and sex), as well as hand size, will be documented. Study staff will verify participant eligibility in the study in-person or over a video conference call with the

participant. The participant will receive a unique screening number that will be recorded in the Participant Screening Form. The participant responses will be included in the Participant Screening Form.

Successfully enrolled participants will be assigned a unique participant identification number based on the order in which they enroll. If the individual is considered eligible to participate in the study, the participant will proceed to the study activities detailed in section 6.1.2.

### 6.1.2. Hand Sanitizer Application

Participants will first be asked to wash and dry their hands and wait an additional two minutes after their hands have dried before application of the hand sanitizer products. Study staff will record that the participant has washed their hands and waited an additional two minutes in the Case Report Form (CRF). The participants will then review the hand sanitizer application steps detailed in Figure 1, which are adapted from the WHO “How to Handrub?” poster.

**Figure 1. Hand Sanitizer Application Steps (Adapted from the WHO “How to Handrub?” Poster)**

The participants will then be instructed by study staff to apply a 1.0 mL or 1.4 mL\* aliquot of Spectrum Advanced Foam to their hands, which will be provided from an automated dispenser, following the hand sanitizer application steps. Study staff will begin to measure the wet time using a calibrated stopwatch: the application of the product to the palm of the participant will indicate the “start time”, and the participant stating that their hands have dried will indicate the “stop time”.

Once the participant has indicated that their hands are dry enough to don medical gloves, study staff will stop the stopwatch and record the Spectrum Advanced Foam wet time in the CRF.

#### **6.1.3. Participant Dismissal**

After the study staff has recorded the wet time of Spectrum Advanced Foam in the CRF, the participant will be dismissed from the study.

### **7. ADVERSE EVENTS (AEs)**

#### **7.1. Definition of AE**

The FDA definition for an AE is: An AE is any unfavorable and unintended sign (including an abnormal laboratory finding), symptom, or disease temporally associated with the use of a medical treatment or procedure that may or may not be considered related to the medical treatment or procedure.

However, a narrower definition of AE will be used for this study. In this study, an AE is any untoward medical occurrence related to the topical use of the hand sanitizers during this study, including skin itching, erythema, edema, or any other skin irritation that occurs.

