#### **7.2. Definition of Serious Adverse Event (SAE)**

The FDA definition of a SAE will be used in this study: An AE or suspected adverse reaction is considered "serious" if, in the view of the PI it results in any of the following outcomes:

- Death,
- A life-threatening adverse event,
- Inpatient hospitalization or prolongation of existing hospitalization,
- A persistent or significant incapacity or substantial disruption of the ability to conduct normal life functions, or

---

*\* The study is to include an interim analysis of the data after 46 participants have completed the study on the medium dispenser setting (1.0 mL). If the results demonstrate a satisfactory 15 second wet time using the medium setting, the study will end and no further recruitment will take place. If at this point, the results demonstrate that the amount of hand sanitizer dispensed under the medium setting (1.0 mL) does not sufficiently stay wet for at least 15 seconds, a second data collection will take place with another 46 participants who will undergo the study using the high dispenser setting (1.4 mL).*

- A congenital anomaly/birth defect.

Important medical events that may not result in death, be life-threatening, or require hospitalization may be considered serious when, based upon appropriate medical judgment, they may jeopardize the participant and may require medical or surgical intervention to prevent one of the outcomes listed in this definition. All SAEs will be reported to Medline, regardless of potential relationship to the study product(s). SAEs will be reported to the reviewing IRB as necessary according to their reporting requirements.

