### **7.4. Relatedness of AE and SAE**

- **Unrelated:** This category applies to those AEs which, after careful consideration, are clearly and incontrovertibly due to extraneous causes (disease, environment, etc.)
- **Possible:** This category applies to those AEs for which, after careful medical consideration at the time they are evaluated, a connection with the Investigational Product administration appears unlikely but cannot be ruled out with certainty.
- **Probable:** This category applies to those AEs which, after careful medical consideration at the time they are evaluated, are felt with a high degree of certainty to be related to the study product(s).
- **Definite:** This category applies to those AEs which, after careful consideration, are clearly and incontrovertibly due to the study product(s).

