## **9. STATISTICAL CONSIDERATIONS**

### **9.1. Sample Size Determination**

The sample size of 46 was estimated for 95% confidence interval based on a standard deviation of 5 seconds and target distance from mean to limits of 1.5 seconds (PASS-Confidence Intervals for One Mean). Results from a previous study conducted by Ecolab (summarized in the Appendix) was utilized as a starting point sample size estimation for the current protocol, using PASS 2021 Power Analysis and Sample Size Software (2021). NCSS, LLC. Kaysville, Utah, USA, [ncss.com/software/pass](http://ncss.com/software/pass). In the event that a participant withdraws from the study, additional participants will be enrolled to achieve a final number of 46 participants with complete data and until adequate power for analysis has been reached.

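### Section 7.1 makes relatedness to the sanitizer part of the AE definition, which conflicts with the Section 7.4 scale that grades AEs as *Unrelated* and leaves Section 7.2 ambiguous

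*Combined protocol and SAP*

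**What the plan says.** All references are to the combined protocol and SAP.

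- **Section 7.1 (definition of AE).** The section opens with the FDA definition, which covers events temporally associated with a treatment or procedure "that may or may not be considered related to the medical treatment or procedure". It then sets that aside: "However, a narrower definition of AE will be used for this study". The replacement is that "an AE is any untoward medical occurrence related to the topical use of the hand sanitizers during this study", followed by itching, erythema, edema and other skin irritation, introduced as included items.
- **Section 7.2 (definition of SAE).** The section says the FDA definition of an SAE applies. That definition takes an AE or a suspected adverse reaction and adds a serious outcome. On reporting, it says "All SAEs will be reported to Medline, regardless of potential relationship to the study product(s").
- **Section 7.4 (relatedness of AE and SAE).** There are four categories. For *Unrelated*: "This category applies to those AEs which, after careful consideration, are clearly and incontrovertibly due to extraneous causes". For *Possible*, the category covers AEs where "a connection with the Investigational Product administration appears unlikely but cannot be ruled out with certainty".
- **Section 7.6 (AE reporting).** Study staff record AEs on the AE form and the investigator reviews them.

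**The concern.** The AE definition decides which events enter the record. The relatedness scale is then applied to what is in the record. If relatedness is a condition of entry, the scale is being asked to grade something already settled, and its lower categories no longer match the events that can reach it.

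At stake is which non-serious events are recorded and put before the investigator. A concrete case follows from Section 6.1.2: each participant washes and dries their hands, waits two minutes, and then applies the foam. Skin irritation afterwards could come from either step. Under Section 7.4 that attribution belongs on a recorded scale. Under Section 7.1 it also determines whether the event is an AE at all. Section 10.a.ii names AE review as the means of finding a risk that may warrant suspending or terminating the study, and that review would see only events that met the narrower definition.

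**Working it through.** No arithmetic bears on this point; the check is a comparison of the sections as they stand.

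**Step 1. Does Section 7.1 require relatedness?** Yes. The contrast is explicit: a definition indifferent to relatedness is cited, a narrower one is announced, and the narrower one adds the condition that the occurrence be related to topical use of the sanitizer. The skin signs come after the word *including*, so they are examples of related occurrences, not a second route into the definition.

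**Step 2. Set Section 7.1 against Section 7.4.**

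| Event | AE under the study definition in 7.1? | Category in 7.4 |
|---|---|---|
| Non-serious, clearly due to an extraneous cause | No | *Unrelated*, which is worded as a class of AEs |
| Non-serious, connection unlikely but not excluded | Unclear | *Possible*, also worded as a class of AEs |
| Non-serious, high certainty of a connection | Yes | *Probable* |
| Non-serious, clearly due to the product | Yes | *Definite* |

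The first row is a direct conflict: 7.4 provides a category for AEs that 7.1 says are not AEs. The second row is a poor fit, because an event whose connection appears unlikely is hard to describe as related. The last two rows agree.

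**Step 3. Consequence for recording.** Section 7.6 asks for AEs to be recorded and then reviewed. An event outside the 7.1 definition is not an AE, so 7.6 does not require a form, and the investigator's assessment under 7.4 need not take place.

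**Step 4. Set Section 7.1 against Section 7.2.** Two readings are open.

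- *Narrow reading:* AE in 7.2 carries the study meaning from 7.1. A serious event thought unrelated then falls outside the SAE definition unless it counts as a suspected adverse reaction, and the instruction to report regardless of relationship has little to act on.
- *Broad reading:* 7.2 names the FDA as the source of its own definition, so AE there carries the FDA meaning. Every serious event is then reportable.

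The text does not say which meaning of AE applies in 7.2. Someone who reports every serious event satisfies its reporting sentence on either reading, so 7.2 can be followed; it is only unclear.

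**Step 5. Does any planning figure depend on this?** No. Section 9.1 gives a 95% confidence interval, a standard deviation of 5 seconds and a half-width of 1.5 seconds. With half-width = t(0.975, n − 1) × 5 / √n, the result is 1.502 s at n = 45 and 1.485 s at n = 46, so the stated 46 is reproduced. No AE quantity enters it.

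**The case against.** The strongest defence is that the narrowing is deliberate and disclosed, and that a sponsor may make that choice in a minimal-risk study of a commercially available product. On that view Chapter 7 has a coherent intention: non-serious events are limited to product-related ones, serious events are not, and one clarifying sentence would be enough.

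Much of this stands. It does not remove the conflict with Section 7.4, which grades AEs generally and gives them an *Unrelated* category. A sentence confining the narrowing to non-serious events would settle 7.2 but leave that category without non-serious events to grade.

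A reader might infer more than the documents support:

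- **That staff are told to judge causality before recording.** Section 7.1 says related, not already judged related, and no section instructs staff to screen events. A prior judgement is a practical consequence of the wording, not a stated procedure.
- **That *Unrelated* can never be used.** Section 7.4 is headed for both AEs and SAEs, so on the broad reading of 7.2 the category has a use for serious events. The conflict is established for non-serious events.
- **That Sections 7.1, 7.2 and 7.4 cannot all be followed on serious events, so unrelated ones would go unreported.** Section 7.2 names its own source definition and asks for reports whatever the relationship. Reporting every serious event complies with it.
- **That a planned safety analysis would be biased.** Section 9.3 plans no safety population, Section 9.5.2 lists no secondary endpoint, and Section 9.8 names no AE analysis.

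The closing words of the skin-sign list, which extend to other irritation that occurs, might be read as capturing any skin event whatever its cause. Because the list illustrates related occurrences, that is not the natural reading. Even if it were adopted, non-skin events would remain outside unless related.

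**Conclusion.** The inconsistency between Sections 7.1 and 7.4 is real for non-serious events, and Section 7.2 is ambiguous about which meaning of AE it uses. The conclusion rests on two readings: that the study definition in 7.1 replaces the FDA one, as the section says, and that the skin signs are examples of related events.

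The practical effect is expected to be small. Participation lasts about 30 minutes, Section 2.3.1 describes minimal risk, and few events of any kind are likely. The documents give no expected event rate, so the number of unrecorded events cannot be estimated. The point still goes beyond a clerical edit, because the wording determines which events are recorded, which reach the investigator, and what the AE review in Section 10.a.ii can see. It is a minor point, worth correcting because the correction is cheap.

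**What to change.** 1. **Section 7.1.** Remove the narrowing and use the FDA definition already cited there: events temporally associated with use of the product, whether or not related. Keep itching, erythema, edema and other skin irritation as examples. The cited definition has no limit to the visit itself, so the revision should not add one by accident.
2. **Sections 7.4 and 7.6.** State that the investigator assigns relatedness, on the 7.4 scale, to every recorded event.
3. **Section 7.2.** State that serious events are reported to the sponsor whatever their relationship to the product, so that the rule no longer depends on which meaning of AE is carried over.

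The three sections then agree. The cost is a short wording amendment and possibly a few extra AE forms. Endpoint, sample size and analysis are unchanged.

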#### **7.2. Definition of Serious Adverse Event (SAE)**

The FDA definition of a SAE will be used in this study: An AE or suspected adverse reaction is considered "serious" if, in the view of the PI it results in any of the following outcomes:

- Death,
- A life-threatening adverse event,
- Inpatient hospitalization or prolongation of existing hospitalization,
- A persistent or significant incapacity or substantial disruption of the ability to conduct normal life functions, or

---

*\* The study is to include an interim analysis of the data after 46 participants have completed the study on the medium dispenser setting (1.0 mL). If the results demonstrate a satisfactory 15 second wet time using the medium setting, the study will end and no further recruitment will take place. If at this point, the results demonstrate that the amount of hand sanitizer dispensed under the medium setting (1.0 mL) does not sufficiently stay wet for at least 15 seconds, a second data collection will take place with another 46 participants who will undergo the study using the high dispenser setting (1.4 mL).*

- A congenital anomaly/birth defect.

Important medical events that may not result in death, be life-threatening, or require hospitalization may be considered serious when, based upon appropriate medical judgment, they may jeopardize the participant and may require medical or surgical intervention to prevent one of the outcomes listed in this definition. All SAEs will be reported to Medline, regardless of potential relationship to the study product(s). SAEs will be reported to the reviewing IRB as necessary according to their reporting requirements.

### **7.3. Severity of AE**

The severity of all AEs will be graded on a scale of one through five according to the Common Terminology Criteria for AE guideline, where each grade represents a unique clinical description based on this general guideline:

- **Grade 1:** Mild; asymptomatic or mild symptoms; clinical or diagnostic observation only; intervention not indicated.
- **Grade 2:** Moderate; minimal, local or noninvasive intervention indicated; limited age-appropriate instrumental activities of daily living.
- **Grade 3:** Severe or medically significant but not immediately life-threatening; hospitalization or prolongation of hospitalization indicated; disabling; limiting activities of daily living involving self-care.
- **Grade 4:** Life threatening consequences; urgent intervention indicated
- **Grade 5:** Death related to AE

### **7.4. Relatedness of AE and SAE**

- **Unrelated:** This category applies to those AEs which, after careful consideration, are clearly and incontrovertibly due to extraneous causes (disease, environment, etc.)
- **Possible:** This category applies to those AEs for which, after careful medical consideration at the time they are evaluated, a connection with the Investigational Product administration appears unlikely but cannot be ruled out with certainty.
- **Probable:** This category applies to those AEs which, after careful medical consideration at the time they are evaluated, are felt with a high degree of certainty to be related to the study product(s).
- **Definite:** This category applies to those AEs which, after careful consideration, are clearly and incontrovertibly due to the study product(s).

## **7.5. Expectedness**

The PI will be responsible for determining whether an AE or SAE is expected or unexpected. An AE will be considered unexpected if the nature, severity, or frequency of the event is not consistent with the risk information previously described for the study intervention.

## **7.6. AE Reporting**

The AEs will be recorded on the AE form (provided by Medline Industries, LP) by the study staff and reviewed by the PI. Changes in the severity of an AE will be documented to allow an assessment of the duration of the event at each level of severity. Changes in severity will necessitate a new CRF to document the new level of severity. AEs characterized as intermittent require documentation of onset and duration of each episode.

Non-serious AEs will be reported to the IRB per IRB reporting requirements.

## **7.7. SAE Reporting**

The PI shall complete an SAE Form (provided by Medline Industries, LP) and will be responsible for reporting the event to the IRB, if applicable, per the IRB's reporting requirements. The PI is responsible for conducting an evaluation of the SAE and shall report the results of such evaluation to the FDA and to all reviewing IRBs, if applicable, within 10 working days after the PI first receives notice of the effect. Thereafter, the PI shall submit such additional reports concerning the effect as FDA requests.

For questions regarding this process or the event, you may contact your Medline clinical designee or the Medline Director of Clinical Operations:

Name: [name], Clinical Affairs Director  
[contact]  
E-mail: [[contact]](mailto:[contact])

## **8. INTERIM ANALYSES**

The study is to include an interim analysis of the data after 46 participants have completed the study on the medium dispenser setting (1.0 mL). If at this point, the results demonstrate that the amount of hand sanitizer dispensed under the medium setting (1.0 mL) does not sufficiently stay wet for at an average of at least 15 seconds, a second data collection whereby another 46 participants will undergo the study using the high dispenser setting (1.4 mL) will take place. If the results demonstrate a satisfactory average 15 second wet time using the medium setting (1.0 mL) with 46 participants, the study results will be analyzed and it will be decided if an additional study using the 1.4 ml setting is warranted.

## **9. STATISTICAL CONSIDERATIONS**

### **9.1. Sample Size Determination**

The sample size of 46 was estimated for 95% confidence interval based on a standard deviation of 5 seconds and target distance from mean to limits of 1.5 seconds (PASS-Confidence Intervals for One Mean). Results from a previous study conducted by Ecolab (summarized in the Appendix) was utilized as a starting point sample size estimation for the current protocol, using PASS 2021 Power Analysis and Sample Size Software (2021). NCSS, LLC. Kaysville, Utah, USA, [ncss.com/software/pass](http://ncss.com/software/pass). In the event that a participant withdraws from the study, additional participants will be enrolled to achieve a final number of 46 participants with complete data and until adequate power for analysis has been reached.

### **9.2. Randomization**

No randomization is planned at this time.

### **9.3. Populations for Analyses**

The analyses will be performed on the intent to treat (ITT) population which consists of all subjects who participated in the study, meaning they have full data on all covariates as well as the hand sanitizer dry time.

No per protocol, safety, or other analyses groups are planned.

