## **5.3. Strategies for Recruitment and Retention**

Participants will be recruited from an internal database of Medline employees. Participants will have previously participated in studies conducted by Medline, and/or have agreed to be contacted for future studies, as well as possibly via IRB-approved advertisement(s). Potential participants will be screened and enrolled until a total of 46 participants with complete data are obtained. Participants that do not complete study activities will be withdrawn from the study and replaced to meet the desired N = 46.

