## **9.8. Statistical Analysis**

Statistical analyses will be conducted in SAS® software, Version 9.4 or higher of the SAS System for Windows (Copyright © 2013 SAS Institute Inc.) or other appropriate statistical software.  $P < 0.05$  will be considered statistically significant.

All continuous variables will be summarized using the following descriptive statistics: (non-missing sample size), mean, standard deviation, median, maximum and minimum. The frequency and percentages (based on the non-missing sample size) of observed levels will be reported for all categorical measures. 95% confidence intervals will be calculated for all means.

A box-and-whisker plot will be employed to display the mean, interquartile range, range, and any possible outliers for wet-to-dry time.

Spearman correlation analysis will be used to examine possible associations between the key variable of dry time with age, sex, and hand size. Additional t-tests or non-parametric tests will be employed to further examine any significant associations found in the correlational analyses between key and covariate measures.

If the results of the interim analysis of 46 participants on the medium dispenser setting (1.0 mL) does not demonstrate that hands stay sufficiently stay wet for at an average of at least 15 seconds, a second data collection whereby another 46 participants will undergo the study using the high dispenser setting (1.4 mL) will take place. All analyses presented above would then be repeated for the data from an additional 46 participants at the high dispenser setting (1.4 mL).

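### Exposed participants who do not finish belong to no analysis set, and no adverse event summary or denominator is specified that would include them

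*Combined protocol and SAP*

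**What the plan says.** Section 9.3 defines a single analysis set. It is labelled intent to treat, but membership is by completeness: "meaning they have full data on all covariates as well as the hand sanitizer dry time". The section then closes off alternatives: "No per protocol, safety, or other analyses groups are planned".

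Section 5.3 states what happens to anyone who does not finish: "Participants that do not complete study activities will be withdrawn from the study and replaced to meet the desired N = 46". It makes no exception for stopping because of an adverse event. Section 9.1 applies the same logic to the sample size: "additional participants will be enrolled to achieve a final number of 46 participants with complete data".

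Sections 4.1 and 6.1.2 take the stop time from the participant's own statement that the hands are dry. Section 2.3.1 names minor skin irritation as the possible risk, and Section 7.1 builds the study's adverse event definition around skin irritation.

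Section 9.8 lists descriptive statistics, a box plot and correlations of dry time with age, sex and hand size. It names no adverse event table, listing or denominator.

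**The concern.** The adverse event this study defines is also a plausible reason not to finish the task. Someone who feels stinging and rinses the foam off has been exposed but has no dry time. Under the replacement rule a completer takes that person's place.

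For wet time, needing a recorded dry time is understandable. For tolerability, the relevant people are those who received the product, and leaving the set can depend on tolerability itself. What is at stake is any adverse event frequency that the study report may give. If it is calculated on the only set the plan defines, it describes completers and not everyone exposed. With so few participants, one or two omitted people can separate a zero from a non-zero result.

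**Working it through.** **1. The plan's own figure.** Section 9.1 gives N = 46 "based on a standard deviation of 5 seconds and target distance from mean to limits of 1.5 seconds", for a 95% interval. The smallest n satisfying t(0.975, n−1) × 5/√n ≤ 1.5 is:
- n = 45: half-width 1.502 s, just too wide.
- n = 46: half-width 1.485 s, which meets the target.

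So N = 46 reproduces. It is a count of completers chosen for the precision of mean wet time, and nothing below changes it.

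**2. Tracing an exposed non-completer through the plan.**
- Sections 4.1 and 6.1.2: no declaration of dryness, so no stop time and no dry time.
- Section 5.3: withdrawn and replaced.
- Section 9.3: no dry time, so outside the defined set; no other set is planned.
- Section 7: the adverse event is still recorded and reported, since nothing there is limited to completers.
- Section 9.8: no adverse event summary, so no rule saying whether this person counts.

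No section returns this person to an analysis set.

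**3. Size when the withdrawals are for irritation.** The documents give neither an adverse event rate nor a withdrawal rate, so the counts are assumptions. Let w be the number who received product and stopped because of irritation, and assume that no completer had an event. Completers then show 0/46, and all exposed show w/(46 + w). Intervals are exact (Clopper-Pearson) 95%.

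| w | Completers | All exposed | 95% interval, all exposed |
|---|---|---|---|
| 0 | 0/46 = 0% | 0/46 = 0% | 0 to 7.7% |
| 1 | 0/46 = 0% | 1/47 = 2.1% | 0.05 to 11.3% |
| 2 | 0/46 = 0% | 2/48 = 4.2% | 0.5 to 14.3% |
| 3 | 0/46 = 0% | 3/49 = 6.1% | 1.3 to 16.9% |
| 5 | 0/46 = 0% | 5/51 = 9.8% | 3.3 to 21.4% |

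The completer figure stays at 0/46 (interval 0 to 7.7%) whatever w is.

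**4. Size when the withdrawals are for other reasons.** Exposed people without an event can also leave the set, for example after a timing failure or with a missing hand measurement. Assume 1 event among the 46 completers and 2 event-free exposed people replaced. Completers show 1/46 = 2.2%; all exposed show 1/48 = 2.1%. The error now runs the other way and is very small.

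**The case against.** The strongest reply is that the plan contains no safety analysis to distort. Wet time is the only objective and endpoint, Section 9.5.2 lists no secondary endpoint, and Section 9.8 specifies no adverse event frequency. On that view, planning no safety group is simply consistent. This stands to the extent that a reader might infer the plan commits to reporting 0/46. It does not; that figure is what would follow if a report used the only defined set. Section 9.8 does say "The frequency and percentages (based on the non-missing sample size) of observed levels will be reported for all categorical measures", but the variables set out in Section 9.6 are age, sex and hand size, so the sentence does not show that adverse events would be tabulated on completers.

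A second reply is that the events are not lost. This also stands. Under Sections 7.2, 7.6 and 7.7, adverse events go on the form and are reviewed by the investigator, all serious events go to the sponsor, and reporting to the ethics board follows its requirements. A reader might infer from the replacement rule that a withdrawn participant's data are discarded; no section says so. Section 9.7 also promises to quantify missing data and report possible biases, although it does not say that a replaced participant's adverse events will be summarised, or over whom.

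A third reply concerns direction. It is tempting to conclude that the frequency can only be too low. The rule removes non-completers for any reason, so the documents do not support that. A participant with irritation who still declares dryness also stays in the set.

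Finally, the numbers lost may well be zero. The product is applied once, Section 2.3.1 describes minimal risk, Section 5.2 excludes relevant skin conditions and known allergy, and the comparable foam in the Appendix stayed wet for 17.1 seconds on average. This bears on priority. It does not supply the missing denominator.

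**Conclusion.** The point holds as a minor one. The completeness rule in 9.3, its express exclusion of a safety group, and the replacement rule in 5.3 and 9.1 together leave an exposed non-completer outside every analysis set. The gap is in the analysed result, not in the recording or reporting of events.

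Its size cannot be estimated from the documents. The illustration of 2.1% or 4.2% against 0% rests on one or two assumed irritation withdrawals and no events among completers. The brief, minimal-risk exposure suggests that the real effect is small. The primary result, the 15-second decision and the sample size are unaffected.

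**What to change.** In Section 9.3, keep the statement that no per-protocol or other sets are planned, remove the word safety from it, and add: *Adverse events will be listed and summarised by dispenser setting for all participants who received any study product, including those withdrawn or replaced.*

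In Section 5.3, add that a replaced participant's adverse event data and reason for stopping are retained and reported.

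The cost is one sentence in each section, the deletion of one word, and one extra table or listing. Adverse events are already collected under Section 7; the reason for stopping needs only to be noted. No extra participants or procedures are needed.
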